5.2 ALL PATIENT TREATMENT

5.3 Nivolumab

All patients will receive two doses of nivolumab prior to the start of definitive chemoradiation. During induction and for those receiving concurrent nivolumab with chemoradiation, this study will use a fixed dose of nivolumab 240 mg every 2 weeks during RT, with each 2 week period constituting a cycle. The cycle window will be +/- 3 days (See section 5.5).

BrUOG 355: 7/8/17, 7/11/17, 7/20/17, 8/7/17, 8/8/17, 8/14/17, 8/16/17, 8/21/17, 8/22/17, 8/24/17, 8/28/17, 9/5/17, 9/6/17, 9/8/17, 9/11/17, 11/7/17, 11/8/17, 11/19/17 approved DD, 11/20/17, 12/12/17, 12/14/17, 1/29/18, 2/1/18, 2/6/18, 2/7/18, 2/8/18, 2/9/18, 2/12/18, 2/13/18, 3/8/18 all reviews, 3/9/18, 3/13/18, 3/14/18, 3/15/18, 4/19/18, 4/23/18, 5/29/18, 6/5/18, Amendment # 1 7/9/18, Amendment # 2 12/12/18, Amendment #3, 4/6/2020, Amendment #4 5/11/2020

For patients assigned to maintenance nivolumab (cohorts 2 and 3), nivolumab will be administered at a fixed dose of 480 mg every 4 weeks, with each 4-week period constituting cycle. The cycle window will be +/- 3 days

5.4 COHORT ASSIGNMENT:

All patients will continue on treatment within 14 days (+/- 7 days) following the final dose of nivolumab pre-chemoradiation in one of three cohorts:

Cohorts will be enrolled consecutively with all patients being enrolled to cohort 1 (8 patients) after-which enrollment to cohort 2 will open (to enroll 4 patients). Once safety is confirmed in those cohorts, enrollment to cohort 3 will open and enroll the remaining patients up to a total of 24 evaluable patients.

- Cohort ONE: Nivolumab during chemoradiation (total, 8 patients)
 - o Definitive radiation therapy fields will be determined by the treating radiation oncologist.
 - o Two groups of patients (4/group) will be evaluated dependent on the chemoradiation field, with the field determined and documented in advance by the treating radiation oncologist:
 - COHORT 1A: Patients receiving EFRT +/- HDR/LDR brachytherapy. Parametrial boost is per MD discretion
 - COHORT 1B: Patients receiving WPRT +/- HDR/LDR brachytherapy. Parametrial boost is per MD discretion
 - o Nivolumab 240mg IV every 14 days (+/- 3 days) for 3 doses, administered concomitantly during chemoradiation and beginning day 1 of Radiation. Dosing days of nivolumab will be flexible to align with cisplatin dosing.
 - o Standard cisplatin dosing will be utilized during treatment (40 mg/m² weekly for maximum of 6 doses)

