- Cohort TWO: Chemoradiation followed by Nivolumab maintenance for 2 years (total, four patients)
 - o Patients will proceed with definitive chemoradiation alone.
 - o 2-3 weeks following completion, patients will begin Nivolumab 480 mg IV every 4 weeks (+/- 3 days) for a planned duration of 2 years.
- Cohort THREE: Nivolumab 240mg IV during chemoradiation and then as nivolumab monotherapy 480mg IV (beginning no more than 4 weeks post CRT) for 2 years (total, approximately 12 patients to enroll allow for total study)

BrUOG 355: 7/8/17, 7/11/17, 7/20/17, 8/7/17, 8/8/17, 8/14/17, 8/16/17, 8/21/17, 8/22/17, 8/24/17, 8/28/17, 9/5/17, 9/6/17, 9/8/17, 9/11/17, 11/7/17, 11/8/17, 11/19/17 approved DD, 11/20/17, 12/12/17, 12/14/17, 1/29/18, 2/1/18, 2/6/18, 2/7/18, 2/8/18, 2/9/18, 2/12/18, 2/13/18, 3/8/18 all reviews, 3/9/18, 3/13/18, 3/14/18, 3/15/18, 4/19/18, 4/23/18, 5/29/18, 6/5/18, Amendment # 1 7/9/18, Amendment # 2 12/12/18, Amendment #3, 4/6/2020, Amendment #4 5/11/2020

enrollment of up to total 24 patients on study)

- Patients will receive nivolumab during definitive chemoradiation (as in cohort one) followed by nivolumab alone (as in cohort two). Pending safety data of cohort one, patients may be stratified by the radiation field, as in cohort One.

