Immune mediated: Adverse events (both serious and non-serious) associated with nivolumab may represent immunologic etiology. Nivolumab must be held for suspected immune-mediated toxicities or severe/life-threatening AEs of particular interest (in Section 7.0) and immune-related toxicities (in Appendix D). Please review both Sections (7 and Appendix D) prior to infusion of nivolumab in any patient in whom immune-mediated toxicity is suspected.

If the investigator is unsure if a particular toxicity at least possibly represents an immune mediated toxicity to nivolumab, the treating physician should follow section 7 and appendix D and treat as immune mediated, until it is confirmed as not being immune mediated. Consultation with BrUOG is suggested in such situations. BrUOG will share information about the situation with the BrUOG Reviewer and PI and provide the site guidance, as available.

Removal from study (all cohorts):

Patients must discontinue nivolumab permanently for the following:

- Any Grade 2 drug-related uveitis or eye pain or blurred vision that does not respond to topical therapy and does not improve to Grade 1 severity within the re-treatment period OR requires systemic treatment
- Grade 3 drug-related thrombocytopenia > 7 days or associated with bleeding
- Any treatment delay resulting in no nivolumab dosing for > 6 weeks.
- Patients who discontinue nivolumab during definitive chemoradiation (cohorts one and three)
- Grade 4 drug-related endocrinopathy adverse events such as adrenal insufficiency, ACTH deficiency, hyper- or hypothyroidism, or glucose intolerance, hypophysitis.
- \geq Grade 4 hepatic AEs
- \geq Grade 4 skin toxicity (per Appendix D can delay or discontinue for grade 3. Must come off, as per this bullet for grade 4 skin)
- ALL OTHER treatment related grade 3/4 treatment related events with the following exceptions:
 - Grade 4 neutropenia \leq 7 days;
 - Grade 4 lymphopenia or leukopenia;
 - isolated Grade 4 electrolyte imbalances/abnormalities that are not associated with clinical sequelae and are corrected with supplementation/appropriate management within 72 hours of their onset;
 - Grade 3 hepatic AEs that return to Grade 2 or less within 5 days Of note, this overrides Appendix D
 - Skin toxicity \leq grade 3 that improves with steroid therapy. NOTE: Any rash consistent with Stevens-Johnson Syndrome or Toxic Epidermal Necrolysis requires permanent discontinuation of nivolumab.
 - Grade 3 renal toxicity (as per Appendix D)

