If Nivolumab is discontinued, the patient is to be taken off study. The total treatment patient BrUOG 355: 7/8/17, 7/11/17, 7/20/17, 8/7/17, 8/8/17, 8/14/17, 8/16/17, 8/21/17, 8/22/17, 8/24/17, 8/28/17, 9/5/17, 9/6/17, 9/8/17, 9/11/17, 11/7/17, 11/8/17, 11/19/17 approved DD, 11/20/17, 12/12/17, 12/14/17, 1/29/18, 2/1/18, 2/6/18, 2/7/18, 2/8/18, 2/9/18, 2/12/18, 2/13/18, 3/8/18 all reviews, 3/9/18, 3/13/18, 3/14/18, 3/15/18, 4/19/18, 4/23/18, 5/29/18, 6/5/18, Amendment # 1 7/9/18, Amendment # 2 12/12/18, Amendment #3, 4/6/2020, Amendment #4 5/11/2020

received will be collected, but once patient is off study, all treatment is per standard of care and does not need to follow-BrUOG 355.

In situations when RT is not given (held for toxicity or other reasons (weather, machine is down, holiday), cisplatin and Nivolumab should not be given and should also be held.

If Nivolumab is held on a day Cisplatin is due and the patient meets criteria to receive Cisplatin and Radiation then every attempt should be made to administer Cisplatin and radiation, while holding Nivolumab.

Every attempt should be made for all patients to complete radiation therapy (even if cisplatin and nivolumab are held)

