approval /favorable opinion of the IRB/IEC. The investigator will submit all protocol modifications to BMS and the regulatory authority (ies) in accordance with the governing regulations. Any departures from the protocol must be fully documented in the source documents.

14.4 On-site Audits:

Regulatory authorities, the IRB and/or BMS clinical quality assurance group may request access to all source documents, data capture records, and other study documentation for on-site audit or inspection. Direct access to these documents must be guaranteed by the investigator, who must provide support at all times for these activities.

14.5 Drug Accountability:

Accountability for the drug at all study sites is the responsibility of the principal investigator. The investigator will ensure that the drug is used only in accordance with this protocol. Drug accountability records indicating the drug's delivery date to the site (if applicable), inventory at the site (if applicable), use by each patient, and return to BMS for disposal of the drug (if applicable and if approved by BMS) will be maintained by the clinical site. Accountability records will include dates, quantities, lot numbers, expiration dates (if applicable), and patient numbers.

All material containing Nivolumab will be treated and disposed of as hazardous waste in accordance with governing regulations.

14.6 Premature Closure of the Study:

This study may be prematurely terminated, if in the opinion of the investigator or BMS, there is sufficient reasonable cause. Written notification documenting the reason for study termination will be provided to the investigator or BMS by the terminating party.

Circumstances that may warrant termination include, but are not limited to:

- Determination of unexpected, significant, or unacceptable risk to patients
- Failure to enter patients at an acceptable rate
- Insufficient adherence to protocol requirements
- Insufficient complete and/or evaluable data
- Plans to modify, suspend or discontinue the development of the drug
- Should the study be closed prematurely, all study materials must be returned to BMS

14.7 Record Retention:

The investigator will maintain all study records according to ICH-GCP and applicable regulatory requirement(s).

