16.1.1. Safety review

A safety review for each cohort will be conducted. For cohort 1, safety analysis will occur at the end of chemoradiation. For patients in cohort 2 (who receive nivolumab following chemoradiation), evaluation for safety will occur 4 weeks following initiation of maintenance nivolumab. For patients in cohort 3, safety analyses will occur at the end of chemoradiation and after maintenance therapy has completed.

Criteria that will determine safety will include:

- Grade 3 or higher adverse events that persists for 14 days or longer despite dose-holds and/or maximal medical support. This excludes uncomplicated neutropenia and any laboratory abnormalities deemed by the treating clinician as having no clinical significance
- Inability to complete chemoradiation within 8 weeks

The BrUOG overall PI, the Women & Infants' Hospital site PI (once study is activated), and the Medical Director of BrUOG will review safety data as described to make determinations of feasibility. Enrollment to cohort 2 will not be dependent on the safety review for cohort 1. However, the safety review will be completed for cohort 2, before enrollment begins in cohort 3.

If more than 25% of patients (more than 2 patients in cohort 1 or more than 1 patient in cohort 2) experience a grade 3 or higher adverse event that persists for 14 days or longer, despite dose-holds and/or maximal support, the treatment will be considered not feasible and the next cohort will not be opened.

If more than 25% of patients (more than 2 patients in cohort 1 or more than 1 patient in cohort 2) are unable to complete chemoradiation within 8 weeks, the treatment will be considered not feasible and the next cohort will not be opened.

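### Section 16.1.1 ties the 25% limit only to opening the next cohort: for cohort 1 that consequence contradicts another sentence, and in neither cohort does a breach require a decision about patients still on nivolumab

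*Combined protocol and SAP*

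**What the plan says.** Section 16.1.1 sets two criteria: a grade 3 or higher adverse event lasting at least 14 days despite holds or maximal support, and failure to finish chemoradiation within 8 weeks. The limit for each is more than 25% of patients, spelled out as more than 2 in cohort 1 and more than 1 in cohort 2. Both rules end identically: "the treatment will be considered not feasible and the next cohort will not be opened".

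The same section also states: "Enrollment to cohort 2 will not be dependent on the safety review for cohort 1". The cohort 2 review must be finished before cohort 3 enrols, and section 5.4 opens cohort 3 only after safety is confirmed in cohorts 1 and 2.

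Cohort 1 is reviewed at the end of chemoradiation, and cohort 2 four weeks after maintenance starts. Three named roles make the feasibility determination.

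On exposure, section 5.4 gives cohort 1 "Nivolumab 240mg IV every 14 days (+/- 3 days) for 3 doses, administered concomitantly during chemoradiation". In cohort 2, "patients will begin Nivolumab 480 mg IV every 4 weeks (+/- 3 days) for a planned duration of 2 years".

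**The concern.** When a third cohort 1 patient or a second cohort 2 patient meets a criterion, later patients cannot reverse the verdict. The regimen is by definition not feasible, yet the plan states one operational consequence, and it concerns a different cohort.

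For cohort 1 the next cohort is cohort 2, whose enrolment is expressly independent of the cohort 1 review. The two sentences cannot both be followed.

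For patients already in the breached cohort, no pause, early review or recorded decision is attached to the count. They are treated with curative intent and may have concurrent doses left, or most of a two-year maintenance course. Continuing may be right for them, but the plan does not make anyone decide.

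**Working it through.** **The plan's own figures.** The largest counts not exceeding 25% are 2 of 8 and 1 of 4, so a breach is 3/8 = 37.5% or 2/4 = 50%. These match the text. The cohorts sum to 8 + 4 + 12 = 24, as stated.

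**Chance of a breach.** The documents give no expected failure rate. I assume 40%, with 25% to 50% as the range.
- Cohort 1: 1 − [0.6⁸ + 8(0.4)(0.6⁷) + 28(0.4²)(0.6⁶)] = 1 − [0.0168 + 0.0896 + 0.2090] = 0.685 (range 0.321 to 0.855).
- Cohort 2: 1 − [0.6⁴ + 4(0.4)(0.6³)] = 1 − [0.1296 + 0.3456] = 0.525 (range 0.262 to 0.688).

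**Timing at 4 a month (section 16.2).** Patients enter (52/12)/4 = 1.08 weeks apart on average.
- The eighth patient enters at 7 × 1.083 = 7.6 weeks.
- If cohort 2 follows without a gap, its four patients enter at 8 × 1.083 = 8.7 to 11 × 1.083 = 11.9 weeks.
- Chemoradiation starts 3 to 5 weeks after entry and lasts 6 weeks to 60 days, so it ends 3 + 6 = 9 to 5 + 60/7 = 13.6 weeks after entry. For the eighth patient that is 16.6 to 21.2 weeks.

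Both cohorts would therefore usually be full before the cohort 1 review is complete. The question is mainly about patients on treatment.

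**Cohort 1 simulation.** 200,000 runs per scenario, with Poisson accrual. From entry: induction at weeks 0 and 2, and concurrent nivolumab at weeks 4, 6 and 8. An adverse-event failure is known 14 days after onset; an 8-week failure is known at week 12. Onset is assumed to be spread over weeks 0–12 or 4–12. Results at the breach, for a 40% rate and 4 a month (25% to 50% in brackets):

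| | Onset 0–12 | Onset 4–12 |
|---|---|---|
| Patients not known to have failed, third concurrent dose still due | 1.8 (1.4–2.2) | 1.1 (0.8–1.4) |
| Concurrent doses left between them | 3.4 (2.5–4.2) | 1.7 (1.2–2.2) |
| Any enrolment still to come | 4% (3–6%) | 1.0% (0.7–1.4%) |
| Routine DSMB meeting falls before the last of these doses | 9% (7–11%) | 5% (3–6%) |

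Counting only patients already enrolled, the doses are about 3.2 and 1.65. For the 8-week criterion the patient count is 0.4 (0.3–0.6). If 24 patients take the stated 9 months (24/9 = 2.67 a month), enrolment remains after an adverse-event breach in 14% / 6%.

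**Cohort 2.** Planned maintenance is 104/4 = 26 doses, taken to start at week 12.5. Two of 4 patients are not known to have failed at the breach. Mean doses left for each, at the breach against when the last patient reaches the planned review (about 23.9):
- adverse-event onset weeks 0–17: 25.3 − 23.9 = 1.4
- onset weeks 4–17: 25.1 − 23.9 = 1.2
- onset weeks 12.5–17: 24.3 − 23.9 = 0.4
- 8-week criterion: 25.5 − 23.9 = 1.6

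An earlier review therefore affects about 0.4 to 1.6 of 26 doses. The other 24 are still ahead at a review the plan already schedules. What is missing is an outcome for those patients.

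**What an automatic 14-day hold would remove.** In cohort 1, doses are two weeks apart and skipped doses are not made up (section 5.5.1). Such a hold would permanently remove about 1.6 of the 3.4 remaining doses (onset 0–12), or 1.0 of 1.7 (onset 4–12).

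**The case against.** The strongest reply is that the power to act already exists.
- The DSMB can meet when needed and can change or end the trial (section 15).
- The investigator or the drug's manufacturer may close the study early, one listed ground being "Determination of unexpected, significant, or unacceptable risk to patients" (section 14.6).
- Serious events reach the coordinating group within 24 hours (section 8.7).
- Affected patients are strictly covered: with listed exceptions, treatment-related grade 3/4 events mean permanent nivolumab discontinuation (section 5.5.1), and a toxicity-related radiation hold of 7 days or more means removal (section 6.2).

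Using a cohort count purely as a go/no-go for the next step is also a legitimate choice in a 24-patient pilot. All of this stands and keeps the point minor. It does not close the gap, because each route is discretionary or acts on the affected patient alone, and none refers to the count.

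Three stronger readings are tempting.
- A reader might infer that nothing can stop a breached cohort. The provisions above show otherwise.
- A reader might infer that some 25 maintenance doses per cohort 2 patient would go unreviewed. The planned review at 4 weeks of maintenance comes before about 24 of them.
- A reader might infer that a breach should suspend nivolumab automatically. The adverse-event criterion has no attribution requirement, so cisplatin or radiation toxicity counts. The 8-week limit (56 days) is tighter than the 60 days that section 5.7 accepts, so two cohort 2 patients finishing on days 57 to 60 would trigger it, although cohort 2 chemoradiation is given without nivolumab. The hold would also take about half or more of the remaining concurrent doses from patients without the toxicity before anyone had decided.

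**Conclusion.** The point holds and is minor. Two things are certain from the text. The cohort 1 consequence contradicts the sentence on cohort 2 enrolment, and no decision about patients still on nivolumab is tied to crossing the limit in either cohort.

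The benefit of repair is modest: in cohort 1, a timely decision for about 1 to 2 patients with about 2 to 3 concurrent doses left after an adverse-event breach, and fewer after an 8-week breach. In cohort 2, the gain is mainly a defined outcome for a review that already takes place. Almost no enrolment is saved at 4 a month.

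The cohort 1 sizes depend on the assumed failure rate and onset windows. The cohort 2 figure barely does, because the review comes 4 weeks into a 104-week course. Patients not known to have failed at the breach may still fail later. The plan gives no count for cohort 3, and this point does not supply one.

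**What to change.** Add to section 16.1.1:

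*The count is kept continuously. When a third patient in cohort 1, or a second in cohort 2, meets the same criterion, any remaining enrolment to that cohort pauses. The named reviewers promptly (within 14 days at most) review the data, inform the DSMB, and record whether and how patients still on treatment continue nivolumab. Chemoradiation continues.*

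Leave any nivolumab hold to the reviewers, and add:

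*A hold decided under this rule is not a discontinuation and does not count towards the 6-week limit in section 5.5.1.*

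This is needed because one skipped 4-weekly dose leaves 8 weeks between doses. Section 5.5.1 lists "Any treatment delay resulting in no nivolumab dosing for > 6 weeks" as a reason for permanent discontinuation, and then "If Nivolumab is discontinued, the patient is to be taken off study". Continuing chemoradiation during a hold is already protocol practice: "every attempt should be made to administer Cisplatin and radiation, while holding Nivolumab".

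Replace the cohort 2 sentence with:

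*Cohort 2 may open before the cohort 1 review is complete; if the cohort 1 limit is crossed, the review decides whether cohort 2 enrolment is held, and cohort 3 is not opened.*

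This agrees with section 5.4. The existing limits stay. The cost is a short added passage and one reworded sentence, a short enrolment pause and one unscheduled review if a limit is crossed, and no extra patients.

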16.2 Sample Size, Accrual Rate and Study Duration

For this feasibility study, the planned sample size is 24 patients (8 in cohorts 1 (1A and 1B)), 4 in cohort 2, and up to 12 in cohort 3 to enroll a maximum of 24 evaluable patients in the trial). The total sample size may need to be adjusted to allow for replacement of participants who withdraw prior to completion of the third week of chemoradiation, as these are the only reasons for replacement. It is anticipated that 4 patients will be enrolled per month for an approximate accrual period of 9 months. All patients who begin protocol therapy will be included in the evaluation of toxicity for 30 days post last treatment, unless patient withdraws from study.

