16.4 Analysis of Primary Endpoints

Time-to-event endpoint of progression free survival at 3 years will be described using the method of Kaplan-Meier, and presented with 90% confidence intervals. Patients that are alive without disease progression at time of analysis are censored at the date of last disease evaluation. Acute Treatment-related toxicities that occur during and within six months of study treatment will be summarized by maximum grade and by term using CTCAE v4.0 and reported with 90% binomial exact confidence intervals. Acute toxicities will be used to determine the feasibility within each cohort.

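### Section 16.1.1 applies its 25% limit to two failure criteria separately and does not clearly count a rapidly fatal event, so a cohort in which half the patients fail can avoid the not-feasible limit

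*Combined protocol and SAP*

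**What the plan says.** Section 16.1.1 names two criteria for the safety review of each cohort. The first is "Grade 3 or higher adverse events that persists for 14 days or longer despite dose-holds and/or maximal medical support", with exclusions for uncomplicated neutropenia and for laboratory findings judged to have no clinical significance. The second is failure to finish chemoradiation within 8 weeks.

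Two separate sentences then set the limit. Each begins "If more than 25% of patients (more than 2 patients in cohort 1 or more than 1 patient in cohort 2" and closes the bracket there. One continues with patients who "experience a grade 3 or higher adverse event that persists for 14 days or longer, despite dose-holds and/or maximal support"; the other with patients who "are unable to complete chemoradiation within 8 weeks, the treatment will be considered not feasible and the next cohort will not be opened". No sentence refers to patients who meet either criterion, and neither mentions death.

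On timing: "For cohort 1, safety analysis will occur at the end of chemoradiation". For cohort 2, "evaluation for safety will occur 4 weeks following initiation of maintenance nivolumab". Section 16.2 gives the sizes: "the planned sample size is 24 patients (8 in cohorts 1 (1A and 1B)), 4 in cohort 2", with up to 12 in cohort 3. Section 16.4 adds: "Acute toxicities will be used to determine the feasibility within each cohort".

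Section 16.1.1 also says that enrolment to cohort 2 does not wait for the cohort 1 review, while the cohort 2 review must be complete before cohort 3 enrols. Cohort 2 is therefore the working gate to the cohort that receives nivolumab both during and after chemoradiation.

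**The concern.** The two criteria are both offered as evidence that the regimen cannot be delivered safely, and a patient who meets either one is a failure in that sense. Testing them one at a time lets failures of different kinds accumulate in different patients without any limit being reached.

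The adverse-event criterion also depends on duration. A patient who finishes chemoradiation on time and dies a few days after the onset of an immune event has had a fatal event that did not, read literally, last 14 days.

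What is at stake is the only numerical rule behind the trial's feasibility conclusion and, through cohort 2, behind the opening of the cohort of up to 12 patients.

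**Working it through.** **The plan's own cut-offs.** For cohort size n the largest count that is not more than 25% is m = floor(0.25 × n). This gives m = 2 for n = 8 and m = 1 for n = 4, so the stated limits of more than 2 and more than 1 reproduce exactly.

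**Largest failing proportion that crosses neither limit.** With separate tests this is 2m patients, reached when the two kinds of failure fall in different patients:
- Cohort 1: 2 + 2 = 4 of 8 = 50%.
- Cohort 2: 1 + 1 = 2 of 4 = 50%.

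**How often it matters.** The documents give no rates and no overlap, so both are assumed here. Let a patient fail the first criterion only, the second only, both, or neither, with probabilities p1, p2, p12 and p0. For counts a, b, c and d of these, the probability is n!/(a! b! c! d!) × p1^a × p2^b × p12^c × p0^d. The separate rule is not crossed when a + c ≤ m and b + c ≤ m. A rule that counts each patient once is not crossed when a + b + c ≤ m.

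Probability of crossing no limit, with a 20% rate for each criterion:

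| Cohort | Overlap between criteria | Patients failing at least one | Separate | Each patient once |
|---|---|---|---|---|
| 1 (n = 8) | none | 40% | 0.61 | 0.32 |
| 1 | independent | 36% | 0.64 | 0.40 |
| 1 | half | 30% | 0.68 | 0.55 |
| 1 | complete | 20% | 0.80 | 0.80 |
| 2 (n = 4) | independent | 36% | 0.67 | 0.55 |

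Hand check of the last cell: 0.64^4 + 4 × 0.36 × 0.64^3 = 0.168 + 0.377 = 0.545.

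**Deaths.**
- *Before chemoradiation is complete, either cohort.* The patient has not completed it, so the second criterion already counts her.
- *After completion.* Only the adverse-event criterion can count her, and its 14-day wording leaves this open. The gap lies mainly in the cohort 2 window, which runs to 4 weeks of maintenance. The cohort 1 review falls at the end of chemoradiation, so a later death may lie outside it altogether.
- *Two deaths in cohort 1, with no other failures.* 2/8 = 25%, which is not more than 25%, whether the deaths are counted under one criterion, both or neither.
- *Two deaths in cohort 2.* 2/4 = 50% crosses the limit if the deaths are counted under the same criterion. Both go uncounted only if they follow completed chemoradiation and the 14-day wording is taken literally.

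**The case against.** A reader might infer that the plan declares a half-failing cohort feasible, or that it makes no provision for deaths. The documents support neither reading.

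- Section 16.1.1 says only when treatment is not feasible. It does not say that staying under both limits means feasible. Its list of criteria is worded as open, and two investigators and the group's Medical Director make the determination.
- Section 5.4 opens cohort 3 only after safety has been confirmed in the earlier cohorts. Section 16.3 allows cohort 3 enrolment to be revised on cohort 1 outcomes.
- Grade 3 or higher has no upper bound, so it can be read to include fatal events. Sections 8.7 and 8.8 require treatment-related deaths to be reported within 24 hours, the DSMB in section 15 can hold extra meetings, and section 14.6 permits closure for unacceptable risk.

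All of this stands, and it limits the claim to what the automatic limit misses. It does not remove the gap, because none of these safeguards sets a count.

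A second objection is that the two criteria are linked. Section 6.2 holds radiation for grade 3 or higher gastrointestinal toxicity, and a toxicity hold of 7 days or more removes the patient from protocol, so one event can produce both failures. This also stands, and it is why the half and complete overlap rows are shown. It has less force in cohort 2, where an event that starts during maintenance cannot have delayed chemoradiation already finished.

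Third, the plan states 25% per criterion and no combined rate. Using the same cut-off for either failure is a stricter rule than the plan contains. That is true, and it is a cost of the change.

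**Conclusion.** The concern holds as a gap in the written rule. Up to 50% of a cohort can fail without crossing the limit, but only if the failures fall in different patients and split equally between the criteria; 4 of 8 failing the same criterion would cross it. This bound is arithmetic and needs no outside assumption. The probabilities rest on assumed rates and overlap: at 20% each the difference in cohort 1 runs from about 0.30 with no overlap to zero with complete overlap, and in cohort 2 it is about 0.13 under independence.

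On deaths, the defect is narrower than an absence of any provision. A rapidly fatal event after completed chemoradiation is not clearly counted, and two deaths in cohort 1 do not reach the limit on any reading.

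This should be fixed. It does not invalidate the design, because discretionary oversight remains and the plan claims no error rates for this pilot.

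**What to change.** In section 16.1.1, define a safety failure as a patient who meets either criterion, or who has a treatment-related grade 5 event of any duration up to that cohort's safety review. Count each patient once, apply the existing limits (more than 2 of 8, more than 1 of 4) to that count, and report the components separately. State that the cohort 1 review includes fatal events known by the time it is held. Leave the response to an individual death to the sponsor and the DSMB.

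The change is wording only and needs no new data. Its cost is a stricter rule. Before any added fatal events, and with independent criteria, the cohort 1 probability of crossing no limit falls from 0.988 to 0.964 at 5% each, and from 0.925 to 0.819 at 10% each. The chance of a not-feasible finding thus rises from 1.2% to 3.6% and from 7.5% to 18.1%. The sponsor should accept that trade knowingly.
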